4.1 INCLUSION CRITERIA

Subjects must meet the following criteria for study entry:

- 1. Diagnosis of CLL:
- Monoclonal B-cells co-expressing ≥ one B-cell marker (CD19, CD20, or CD23) and CD5 in peripheral blood or lymph node.
 - 2. Indication for treatment as defined by the IWCLL Guidelines:
- Massive (i.e. > 6 cm below the left costal margin) or progressive/ symptomatic splenomegaly OR
- Massive lymph nodes or nodal clusters (i.e. > 10 cm in longest diameter), or progressive / symptomatic lymphadenopathy OR
 - Presence of disease-related constitutional symptoms:
 - Weight loss ≥ 10% over the preceding 6 months
- Significant fatigue (i.e., ECOG PS 2 or worse; inability to work or perform usual activities).
- Fevers higher than 100.5°F or 38.0°C for 2 or more weeks without other evidence of infection.
 - Night sweats for more than 1 month without evidence of infection.

Ibrutinib + GA101 – Obinutuzumab. University of California, San Diego

- Progressive lymphocytes with an increase of \geqslant 50% over a 2-month period or an anticipated doubling time of less than 6 months. OR
- Evidence of progressive marrow failure as manifested by the development of, or worsening of, anemia and / or thrombocytopenia.
- Autoimmune anemia and / or thrombocytopenia poorly responsive to corticosteroids or other standard therapy.
 - 3. No previous treatment for CLL.
 - 4. Males and females 65 years of age and older. Subjects < 65 years of age that meet any of the following criteria:
 - Subjects that refuse to be treated with chemotherapy based agents (This should be documented in the consent form).
 - Subjects that are not candidates for treatment with chemotherapy agents based on any of the following:
 - ECOG Performance status ≥ 2
 - Cumulative Illness Rating Scale (CIRS score) ≥ 6 (Appendix 6)
 - Creatinine clearance <70 mL/min using the Cockcroft-Gault Equation.
 - 5. Laboratory parameters as specified below:
 - Hematologic: Hemoglobin \geq 8 g/dL (may be post-transfusion); platelet count \geq 40 x10³/mm³ (may be post-transfusion). Absolute neutrophil count \geq 1.0 × 10⁹ cells/L (Growth factor use is allowed).
 - Hepatic: Total Bilirubin < 3 x ULN, and ALT and AST < 3 x ULN
 - Renal: Creatinine clearance > 30 mL/min (Calculated according to institutional standards or using Cockcroft–Gault formula. Subjects with requirement of hemodialysis will be excluded).
 - 6. Anticipated survival of at least 6 months.
- 7. Effective contraception is required while receiving Ibrutinib in combination with GA101 Obinutuzumab. For women of childbearing potential and men, effective

Ibrutinib + GA101 – Obinutuzumab. University of California, San Diego

contraception is required while receiving GA101 – Obinutuzumab and for 365 days (12 months) after the last dose of the study drug.

- 8. Ability to understand the requirements of the study, provide written informed consent and authorization of use and disclosure of protected health information, and agree to abide by the study restrictions and return for the required assessments.
 - 9. Subjects must give written informed consent to participate in this trial.

4.2 EXCLUSION CRITERIA

Subjects who meet any of the following criteria will be excluded from study entry:

- 1. Pregnant or nursing women.
- 2. Treatment with chemotherapy, monoclonal antibodies or biological agents (e.g. lenalidomide) other than the investigational agents during the time of participation in this trial.
- 3. Grade 3 or 4 cardiac disease as defined by the New York Heart Association Functional Classification.
- 4. Severe or debilitating pulmonary disease (dyspnea at rest, significant shortness of breath, COPD).
- 5. Participation in any investigational drug study within 28 days prior to initiation of treatment within this protocol. (Subject must have recovered from all acute effects of previously administered investigational agents).
- 6. History of second malignancy, other than non-melanoma skin cancer or in situ carcinoma of the cervix or the breast, unless the tumor was successfully treated at least 2 years before trial entry and with no evidence of relapse or active cancer.
- 7. Active symptomatic fungal, bacterial and/or viral infection including evidence of infection with human immunodeficiency virus (HIV).
- 8. Evidence of active acute or chronic Hepatitis B (HBV): Subjects with acute or chronic active HBV will be defined based on CDC guidelines (Appendix 1). This will include subjects with positive serology for hepatitis B surface antigen (HBsAg) or hepatitis B core antibody (anti-HBc) associated with HBV-DNA positive test by real time quantitative qPCR assessment. Subjects, who are anti-HBc positive and HBsAg negative or HBV-DNA test negative, may be enrolled in the study and should undergo

[figure not shown]
Ibrutinib + GA101 – Obinutuzumab. University of California, San Diego

regular monitoring of HBV viral load using HBV-DNA qPCR. Those subjects may be referred to a hepatologist or gastroenterologist for appropriate monitoring and management including antiviral therapy.

- 9. Evidence of active Hepatitis C (HCV): subjects with positive hepatitis C serology and positive HCV RNA test.
- 10. Any illness or condition that in the opinion of the Investigator may affect safety of treatment or evaluation of any the study's endpoints.
- 11. History of severe allergic or anaphylactic reactions to monoclonal antibody therapy.
 - 12. Known hypersensitivity to any of the study drugs.
- 13. Major surgery (within 4 weeks prior to the start of Cycle 1), except for procedures that are performed for diagnostic purposes.
- 14. Men or women of childbearing potential who refuse to use an adequate measure of contraception (oral contraceptives, intrauterine device, or barrier method of contraception in conjunction with spermicidal jelly) unless they have past medical history of surgical sterilization.
- 15. Vaccination with a live vaccine within 28 days of the initiation of treatment.
 - 16. Concomitant use of warfarin or other Vitamin K antagonists.
- 17. Requirement to receive treatment with a strong cytochrome P450 (CYP) 3A inhibitor. Subjects who received a strong cytochrome P450 (CYP) 3A inhibitor within 7 days prior to the first dose of Ibrutinib or subjects who require continuous treatment with a strong CYP3A inhibitor.
- 18. Subjects with chronic liver disease with hepatic impairment (Child-Pugh class B or C).

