- Participation in any investigational drug study within 28 days prior to initiation of treatment within this protocol. (Subject must have recovered from all acute effects of previously administered investigational agents).
- 6. History of second malignancy, other than non-

Ibrutinib + GA101 - Obinutuzumab. University of California, San Diego

- melanoma skin cancer or in situ carcinoma of the cervix or the breast, unless the tumor was successfully treated at least 2 years before trial entry and with no evidence of relapse or active cancer.
- 7. Active symptomatic fungal, bacterial and/or viral infection including evidence of infection with human immunodeficiency virus (HIV).
- 8. Evidence of active acute or chronic Hepatitis B (HBV).
- Evidence of active Hepatitis C (HCV): subjects with positive hepatitis C serology and positive HCV RNA test.
- 10. Any illness or condition that in the opinion of the Investigator may affect safety of treatment or evaluation of any the study's endpoints.
- 11. History of severe allergic or anaphylactic reactions to monoclonal antibody therapy
- 12. Known hypersensitivity to any of the study drugs.
- 13. Major surgery (within 4 weeks prior to the start of Cycle 1), except for procedures that are performed for diagnostic purposes.
- 14. Men or women of childbearing potential who refuse to use an adequate measure of contraception (oral contraceptives, intrauterine device, or barrier method of contraception in conjunction with spermicidal jelly) unless they have past medical history of surgical sterilization.
- 15. Vaccination with a live vaccine within 28 days of the initiation of treatment.
- 16.Concomitant use of warfarin or other Vitamin K antagonists.

17. Subjects who received a strong cytochrome P450 (CYP) 3A inhibitor within 7 days prior to the first dose of Ibrutinib or subjects who require continuous treatment with a strong CYP3A inhibitor.

18. Subjects with chronic liver disease with hepatic impairment (Child-Pugh class B or C)

Dosage and administration

Ibrutinib 420 mg (3 x 140 mg capsules) will be administered orally once daily beginning on Day 1 of the Treatment Phase. The first dose of Ibrutinib 420 mg will be administered in the clinic on Day 1, no more than 72 hours after enrollment, after which Ibrutinib will be self-administered by the subjects on an outpatient basis.

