6.2.10 Hepatitis B Virus Reactivation

Active acute or chronic Hepatitis B (HBV): Subjects with acute or chronic active HBV will be defined based on CDC guidelines (Appendix 1). This will include subjects with positive serology for hepatitis B surface antigen (HBsAg) or hepatitis B core antibody (HBcAb) associated with HBV-DNA positive test by real time quantitative qPCR assessment. Subjects who are anti-HBc positive and HBV-DNA test negative, may be enrolled in the study and should undergo regular monitoring of HBV viral load using HBV-DNA qPCR. Those subjects may be referred to a hepatologist or gastroenterologist for appropriate monitoring and management.

For the subset of subjects who are Hepatitis B viral DNA negative and anti-HBc positive and have undetectable Hepatitis B viral DNA levels at screening, Hepatitis B viral DNA levels must be followed approximately every 4 weeks. Guidelines for the management of hepatitis B reactivation are outlined in Table 2.

Table 2 Management of Hepatitis B Reactivation

Hepatitis B Viral DNA Level by Real-Time PCR	Guideline
> 100 IU/mL	Hold GA101 - Obinutuzumab
	Begin anti-viral medication and treat for at least 1 year after the last dose of GA101 - Obinutuzumab.
	 Immediately refer the subject to a gastroenterologist or hepatologist for management.
	Resume GA101-Obinutuzumab once Hepatitis B viral DNA levels decrease to undetectable levels.
> 100 IU/mL while on anti-viral medication	Discontinue GA101 - Obinutuzumab.
29-100 IU/mL	Retest within 2 weeks.
	If still hepatitis B viral DNA positive:
	Hold GA101 - Obinutuzumab

Ibrutinib + GA101 – Obinutuzumab. University of California, San Diego

Begin anti-viral medication and treat for at least 1 year after the last dose of GA101 - Obinutuzumab.

 Immediately refer the subject to a gastroenterologist or hepatologist for management

 Resume GA101-Obinutuzumab once Hepatitis B viral DNA levels decrease to undetectable levels

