9.1.2.2 Screening Laboratory Tests

(To be performed within 28 days prior to treatment start date)

- HBsAg, HbsAb, HBcAb (IgG, IgM), HAAb and Hepatitis CAb. (If HBcAb is positive an HBV-DNA viral load qPCR test will be performed)
 - HIV serology
 - CBC, differential, platelet count, PT, PTT, INR; AND
- comprehensive metabolic panel including: Total bilirubin, AST (SGOT), ALT (SGPT), alkaline phosphatase, albumin, creatinine, BUN, total protein, fasting blood glucose, calcium, sodium, potassium, chloride, HCO3, phosphorus, LDH and uric acid; AND

Ibrutinib + GA101 - Obinutuzumab. University of California, San Diego

- Beta-2 microglobulin AND
- Quantitative immunoglobulin levels (IgG, IgA, IgM) AND
- Immunophenotyping of blood mononuclear cells: CD3, CD4, CD5, CD8, CD19, CD20.
- Absolute T cell count including CD3+, CD4+, and CD8+ populations; AND
- Serum Pregnancy Test (HcG levels) for FCBP (females of child bearing potential)

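### Exclusion 8 both excludes and admits a subject who is anti-HBc positive, HBsAg negative and HBV-DNA positive, and Section 6.2.10 states a different admitting rule

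*Combined protocol and SAP*

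**What the plan says.** Section 4.2 opens its list with "Subjects who meet any of the following criteria will be excluded from study entry". Exclusion 8 covers active acute or chronic hepatitis B and refers to the CDC table in Appendix 1. It then spells out who counts as active: positive serology for HBsAg, or "hepatitis B core antibody (anti-HBc) associated with HBV-DNA positive test by real time quantitative qPCR assessment".

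The sentence that follows admits some subjects: "Subjects, who are anti-HBc positive and HBsAg negative or HBV-DNA test negative, may be enrolled in the study". They are to have regular viral-load monitoring, for which 4.2 gives no interval.

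Section 6.2.10 repeats the definition of active disease, but its admitting sentence is different: "Subjects who are anti-HBc positive and HBV-DNA test negative, may be enrolled in the study". It then requires HBV-DNA about every 4 weeks in anti-HBc-positive subjects whose DNA was undetectable at screening.

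Section 9.1.2.2 governs testing at entry: "If HBcAb is positive an HBV-DNA viral load qPCR test will be performed". Footnote a of the Appendix 2 flowchart says the same. The synopsis gives only the short form of exclusion 8. Section 1.3.4.4 says that obinutuzumab should not be given to subjects with active HBV disease.

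**The concern.** Two consecutive sentences of one exclusion criterion give opposite answers for the same test results. The definition turns on the DNA result. The admitting sentence joins negative HBsAg and negative DNA with an *or*, so a negative HBsAg is enough whatever the DNA result. Section 6.2.10 does not contain that alternative, so the protocol holds two admitting rules.

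What is at stake is safety and consistent eligibility decisions. The DNA test is already done in anti-HBc-positive candidates, so the disputed pattern would be recognised at screening, and the person deciding would find text for both dispositions. A DNA-positive subject enrolled on the second sentence would also fall outside the 4-weekly monitoring in 6.2.10, which is written for subjects with undetectable DNA at screening.

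**Working it through.** The plan gives no figure to reproduce. The check is to run every combination of the three results through the rules as written.

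**Inputs**
- Definition of active HBV (excluded): Section 4.2, exclusion 8, repeated in 6.2.10.
- Admitting sentences: Section 4.2, exclusion 8, and Section 6.2.10.
- Three binary results (anti-HBc, HBsAg, HBV-DNA), so 2 × 2 × 2 = 8 patterns.

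**Readings**
- E1, excluded: (HBsAg+ or anti-HBc+) and DNA+. The DNA condition attaches to both serologies.
- E2, excluded: HBsAg+ or (anti-HBc+ and DNA+). The DNA condition attaches to anti-HBc only.
- A1, admitted under 4.2: anti-HBc+ and (HBsAg− or DNA−).
- A2, admitted under 4.2: (anti-HBc+ and HBsAg−) or DNA−.
- S, admitted under 6.2.10: anti-HBc+ and DNA−.

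| anti-HBc | HBsAg | DNA | E1 | E2 | A1 | A2 | S | Both excluded and admitted |
|---|---|---|---|---|---|---|---|---|
| + | + | + | yes | yes | no | no | no | never |
| + | + | − | no | yes | yes | yes | yes | under E2, with A1, A2 and S |
| + | − | + | yes | yes | yes | yes | no | under all four pairings in 4.2; not with S |
| + | − | − | no | no | yes | yes | yes | never |
| − | + | + | yes | yes | no | no | no | never |
| − | + | − | no | yes | no | yes | no | under E2 with A2 only |
| − | − | + | no | no | no | no | no | never |
| − | − | − | no | no | no | yes | no | never |

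**Results**
1. Anti-HBc+, HBsAg−, DNA+ is excluded and admitted under all 2 × 2 = 4 pairings of readings in 4.2. It is the only pattern of which this is true, so the contradiction does not depend on grammar.
2. With the 6.2.10 wording (S), that pattern is excluded and not admitted. The two sections therefore state different rules.
3. Under E2, anti-HBc+, HBsAg+, DNA− is also excluded and admitted, with both the 4.2 and the 6.2.10 wording. Copying the 6.2.10 sentence into 4.2 would leave that conflict unless the scope of the DNA condition is settled as well.
4. Anti-HBc−, HBsAg+, DNA− conflicts only under E2 with A2. A2 is a strained reading, because the sentence is about anti-HBc-positive subjects.

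**Does Appendix 1 settle it?** No. It uses no DNA result. HBsAg-positive, anti-HBc-positive patterns with negative anti-HBs are labelled acutely or chronically infected, according to IgM anti-HBc. HBsAg-negative, anti-HBc-positive patterns are labelled immune after natural infection if anti-HBs is positive. If anti-HBs is negative they are labelled unclear, with low-level chronic infection among the four possibilities.

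**Size.** The documents give no prevalence of the disputed pattern. Assuming 0 to 3% of candidates, 32 × 0 = 0 and 32 × 0.03 = 0.96, so zero to about one subject. The range is an assumption for scale only.

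**The case against.** The strongest answer is that the intent can be recovered. The lead-in to 4.2 excludes anyone who meets any listed criterion, and an anti-HBc-positive, DNA-positive subject meets the definition in exclusion 8. The later sentence is only permissive and does not claim to override it. Section 6.2.10 admits on negative DNA, 1.3.4.4 advises against obinutuzumab in active disease, and exclusion 10 lets the investigator exclude on safety grounds. The DNA result would be known before entry.

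This stands as evidence of likely intent and limits the practical risk. It does not remove the conflicting sentence, and eligibility should not rest on inference from other sections.

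Three stronger readings are tempting, and the documents do not support them:
- *The protocol plainly lets a viraemic subject start obinutuzumab.* The text contradicts itself, and the lead-in to 4.2 favours exclusion. It is not an open route to treatment.
- *A subject could be eligible at the very DNA level at which Table 2 holds obinutuzumab (above 100 IU/mL).* Exclusion 8 gives no level, only a positive test. Table 2 also has a 29–100 IU/mL retest row, concerns reactivation, and is not said to apply to a screening result.
- *Exactly one pattern conflicts, and 6.2.10 is free of conflict.* This holds under E1 but fails under E2.

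**Conclusion.** The point holds as an internal inconsistency in a safety-relevant entry criterion. Exclusion 8 gives two dispositions for anti-HBc-positive, HBsAg-negative, HBV-DNA-positive subjects under every parsing, and 6.2.10 states a different admitting rule. Whether a second pattern is affected depends on an ambiguity that the text leaves open, namely whether the DNA condition applies to HBsAg as well as to anti-HBc.

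Few subjects are likely to be involved: zero to about one of 32 on the assumed range. The objective response rate, the two-stage decision rule, type I error and power do not depend on it. It should be corrected because the ambiguity falls on a safety criterion and removing it costs little. No view is taken here on which eligibility rule is clinically right.

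**What to change.** Reconcile the two sentences of exclusion 8 with each other, with Section 6.2.10 and with Appendix 1, so that each HBsAg / anti-HBc / HBV-DNA pattern has one disposition. The clinical team should decide the intended rule and state explicitly whether the DNA condition applies to both serologies or to anti-HBc only. The same sentence should then appear in 4.2 and 6.2.10; a short table of the eight patterns would avoid the *and/or* problem.

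The cost is a clause in 4.2 and matching text in 6.2.10. The anti-HBc-positive patterns need no new test, because HBV-DNA is already run for them. If the agreed rule makes the disposition of an HBsAg-positive, anti-HBc-negative subject depend on DNA, the trigger in 9.1.2.2, which is keyed to HBcAb, should be checked at the same time.

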1.3.4.4 Hepatitis B Reactivation

Due to the potential for hepatitis B reactivation to occur with anti-CD20 therapy, all subjects should be screened for hepatitis B virus (HBV) prior to initiation treatment with GA101 - Obinutuzumab. Subjects with positive serology may be referred to a hepatologist or gastroenterologist for appropriate monitoring and management. subjects with active HBV disease should not be treated with GA101 - Obinutuzumab.

Ibrutinib + GA101 – Obinutuzumab. University of California, San Diego

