Appendix 1 CDC Guideline for Interpretation of Hepatitis B Serology Test Results

Interpretation of Hepatitis B Serologic Test Results

Hepatitis B serologic testing involves measurement of several hepatitis B virus (HBV)-specific antigens and antibodies. Different serologic "markers" or combinations of markers are used to identify different phases of HBV infection and to determine whether a patient has acute or chronic HBV infection, is immune to HBV as a result of prior infection or vaccination, or is susceptible to infection.

HBsAg anti-HBc anti-HBs	negative negative negative	Susceptible
HBsAg anti-HBc anti-HBs	negative positive positive	Immune due to natural infection
HBsAg anti-HBc anti-HBs	negative negative positive	Immune due to hepatitis B vaccination
HBsAg anti-HBc IgM anti-HBc anti-HBs	positive positive positive negative	Acutely infected
HBsAg anti-HBc IgM anti-HBc anti-HBs	positive positive negative negative	Chronically infected
HBsAg anti-HBc anti-HBs	negative positive negative	Interpretation unclear; four possibilities: 1. Resolved infection (most common) 2. False-positive anti-HBc, thus susceptible 3. "Low level" chronic infection 4. Resolving acute infection

Adapted from: A Comprehensive Immunization Strategy to Eliminate Transmission of Hepatitis B Virus Infection in the United States: Recommendations of the Advisory Committee on Immunization Practices. Part I: Immunization of Infants, Children, and Adolescents. MMWR 2005;54(No. RR-16).

- DEPARTMENT OF HEALTH & HUMAN SERVICES
 Centers for Disease Control and Prevention
 Division of Viral Hepatitis
 - www.cdc.gov/hepatitis

- Hepatitis B surface antigen (HBsAg): A protein on the surface of hepatitis B virus; it can be detected in high levels in serum during acute or chronic hepatitis B virus infection. The presence of HBsAg indicates that the person is infectious. The body normally produces antibodies to HBsAg as part of the normal immune response to infection. HBsAg is the antigen used to make hepatitis B vaccine.
- Hepatitis B surface antibody (anti-HBs):
 The presence of anti-HBs is generally interpreted as indicating recovery and immunity from hepatitis B virus infection. Anti-HBs also develops in a person who has been successfully vaccinated against hepatitis B.

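### The enrolment permission in 4.2 item 8 literally admits anti-HBc-positive, HBsAg-negative, HBV-DNA-positive subjects, whom the same item excludes and 6.2.10 does not permit

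*Combined protocol and SAP*

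**What the plan says.** Section 4.2 opens by stating that meeting any listed criterion excludes a subject. Item 8 covers active acute or chronic hepatitis B. It refers to the CDC table in Appendix 1 and says that active disease includes positive serology for HBsAg or for "hepatitis B core antibody (anti-HBc) associated with HBV-DNA positive test by real time quantitative qPCR assessment". The permission follows directly, for subjects "who are anti-HBc positive and HBsAg negative or HBV-DNA test negative, may be enrolled", with regular viral-load monitoring.

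Four other places bear on the same rule:

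- Section 6.2.10 repeats the definition but permits on narrower terms: "Subjects who are anti-HBc positive and HBV-DNA test negative, may be enrolled in the study". Its roughly four-weekly HBV-DNA monitoring is written only for anti-HBc-positive subjects whose DNA is undetectable at screening.
- Section 1.3.4.4 states that "subjects with active HBV disease should not be treated with GA101 - Obinutuzumab".
- Section 9.1.2.2 makes HBV-DNA a reflex test at screening: "If HBcAb is positive an HBV-DNA viral load qPCR test will be performed".
- Synopsis exclusion 8 bars active hepatitis B and contains no permission.

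**The concern.** A subject who is anti-HBc positive, HBsAg negative and HBV-DNA positive fits the exclusion and also fits the sentence that allows enrolment. Staff checking eligibility against item 8 alone would find support for either decision.

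The rule protects against a risk that the protocol treats as serious. Hepatitis B reactivation under anti-CD20 therapy has its own risk section (1.3.4.4). It is an adverse event of special interest (11.4.3.7), and reactivation that does not respond to management is a reason for discontinuation (section 7). Table 2 in 6.2.10 requires obinutuzumab to be held when HBV-DNA exceeds 100 IU/mL. A subject admitted on the literal sentence with DNA above that level would meet the hold threshold on entry.

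**Working it through.** The plan states no figure here, so the check is one of logic. Write C for anti-HBc positive, S for HBsAg positive and D for HBV-DNA positive.

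**Inputs**

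- Permission in 4.2 item 8, two groupings: P1 = (C and not S) or not D; P2 = C and (not S or not D).
- Exclusion in 4.2 item 8, two groupings: E1 = (S or C) and D, where the DNA condition applies to both markers; E2 = S or (C and D), where HBsAg positivity alone excludes.
- Permission in 6.2.10: C and not D.

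**The four anti-HBc-positive profiles**

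| HBsAg | HBV-DNA | P1 | P2 | E1 | E2 | 6.2.10 permits |
|---|---|---|---|---|---|---|
| + | + | no | no | excluded | excluded | no |
| + | − | yes | yes | not excluded | excluded | yes |
| − | + | yes | yes | excluded | excluded | no |
| − | − | yes | yes | not excluded | not excluded | yes |

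**Step 1: the contradictory profile.** In the third row, P1 holds through its first limb and P2 holds because HBsAg is negative. Reading *or* as exclusive changes neither result, since exactly one of the two alternatives is true. E1 and E2 both hold because C and D are both true. The profile is therefore permitted on 4 of 4 readings of the permission and excluded on 2 of 2 readings of the exclusion. Among all eight combinations of the three markers, it is the only one that is both permitted and excluded on every reading.

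**Step 2: counts.** With an inclusive *or*, item 8 permits 3 of the 4 profiles under P1 and P2 alike, and 6.2.10 permits 2. The difference, 3 − 2 = 1, is the contradictory profile.

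**Step 3: the second row.** The HBsAg-positive, DNA-negative profile is permitted by both sections. Under E1 it is not excluded, so there is no conflict. Under E2 it is excluded, so both permissions would conflict with it. This result depends on the grouping; the result in step 1 does not.

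**Step 4: candidate wordings for item 8**

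| Item 8 permission | Anti-HBc-positive profiles permitted | Conflicts under E1 | Conflicts under E2 |
|---|---|---|---|
| As written | 3 | 1 | 2 |
| 6.2.10 wording (C and not D) | 2 | 0 | 1 |
| *or* changed to *and* (C and not S and not D) | 1 | 0 | 0 |

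Both changes remove the contradiction in step 1. They differ only on the second row. With *and*, that profile is excluded under E2. Under E1, item 8 neither excludes nor permits it, while 6.2.10 would still permit it unless amended too.

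**The case against.** The strongest reply is that nothing follows in practice. The lead-in to 4.2 makes every criterion mandatory, and a permissive clause inside an exclusion does not cancel it. HBV-DNA is measured at screening in every anti-HBc-positive subject. Sections 6.2.10 and 1.3.4.4 and the synopsis all agree, and item 10 of 4.2 lets the investigator exclude for any condition affecting safety. All of this stands. It shows the intent and keeps the consequence small, but it does not remove a sentence that permits what its own criterion bars.

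Two stronger readings are tempting, and the documents do not support either.

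- A reader might infer that the plan means to enrol viremic subjects. The provisions just listed point the other way, and an *or* written for *and* is the likelier explanation.
- A reader might infer that admitting anti-HBc-positive, HBsAg-positive, DNA-negative subjects is a second proven error. Appendix 1 lends this some support: it says "The presence of HBsAg indicates that the person is infectious", and it classes HBsAg-positive, anti-HBc-positive, anti-HBs-negative results as acute or chronic infection. Section 9.1.2.2 also schedules no DNA test for an HBsAg-positive, anti-HBc-negative subject, so a DNA condition on HBsAg could not operate there. But Appendix 1 has no HBV-DNA row and does not define *active*, the operative word in item 8. Section 6.2.10 is consistent with itself under E1 and contradicts itself under E2. Section 1.3.4.4 separates positive serology, which may lead to referral, from active disease, which bars treatment. Section 7 provides for following hepatitis B carriers who stop study treatment, which is at least compatible with non-viremic carriers being on study. The question is open and belongs to the sponsor.

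**Conclusion.** The point holds, and it is minor. One profile (anti-HBc positive, HBsAg negative, HBV-DNA positive) is both excluded and permitted by 4.2 item 8 on every reading, and 6.2.10 does not permit it. This is a drafting error in a safety eligibility rule.

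The conclusion rests only on the wording of the two sections and needs no assumption about grouping. The judgement that the practical effect is small assumes that sites perform the reflex HBV-DNA test and apply the exclusion over the permission. The documents do not say how often the profile occurs, so no number of affected subjects can be given. The planned 32 subjects, the type I error and the power do not depend on it.

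**What to change.** Make a negative HBV-DNA test mandatory in the item 8 permission, in one of two ways:

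- adopt the 6.2.10 condition: anti-HBc positive and HBV-DNA negative; or
- change *or* to *and*: anti-HBc positive, HBsAg negative and HBV-DNA negative.

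The choice turns on whether anti-HBc-positive, HBsAg-positive, DNA-negative subjects are eligible. Ask the sponsor to decide this, and then use one wording in 4.2 and 6.2.10. If they are eligible, the first option suffices, and the exclusion sentence should make clear that the DNA condition applies to both markers. If they are not, use the second option in both sections and reword the exclusion as HBsAg positive, or anti-HBc positive with detectable HBV-DNA. That second choice is a substantive eligibility change, because this profile would lose the permission that 6.2.10 now gives it.

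Removing the proven contradiction takes a few words at the next amendment. Settling the HBsAg question may also mean editing the definition, which appears in both sections. HBsAg, anti-HBc and reflex HBV-DNA are already screening tests under 9.1.2.2, so no procedure is added and the statistical design is unchanged.
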